5.4 Withdrawal of Subjects

Subjects may withdraw their consent, or voluntarily withdraw from the study at any time without having to provide a reason and without prejudice to further treatment.

The Investigator and Sponsor have the right to withdraw subjects from the study. However, as this is a single dose study, the Sponsor's preference is that subjects remain in the study for as much of the 24-week follow-up period as possible, to maximize the amount of safety and efficacy information collected on EP-104IAR.

Reasons for withdrawing a subject may include:

- Lack of compliance with the protocol or study restrictions
- Occurrence of an AE (serious or non-serious), at the discretion of the Investigator
- At the Investigator's discretion if it is in the subject's best interest

- At the request of the Sponsor, whether for administrative or other reasons
- Sponsor discontinues the study, or a specific site

The reason(s) for withdrawal must be recorded on the subject's electronic case report form (eCRF) and source documentation. If the subject withdraws from the study without providing a reason, the reason for discontinuation should be documented as "withdrawal of consent".

Subjects who are withdrawn from the study prematurely should undergo all End--of--Study (Visit 9) assessments, if possible.

If a subject is discontinued due to an AE/SAE, the event should be followed by the Investigator through contact with the subject until resolution or stabilization has occurred, or the subject is lost to follow-up and cannot be contacted.

Subjects who withdraw or who are removed from the study for any reason after being randomized (whether they received their dose of investigational medicinal product (IMP) or not), will not be replaced.

Imaging Sub-Study

In addition to the reasons for withdrawing a subject from the main study listed above, if a subject participating in the imaging sub-study has an adverse reaction to the contrast agent, becomes pregnant, or develops moderate to severe renal dysfunction (i.e., an eGFR ≤ 40 mL/min/1.73 m²) they should be withdrawn from the imaging sub-study and undergo no further MRI assessments.

Withdrawal from the imaging sub-study does not impact the subject's participation in the main study. However, if a subject participating in the imaging sub-study exits the main study early, they will also be withdrawn from the imaging sub-study. An early exit visit will be performed, and an early exit MRI acquired on or immediately following the visit. If the early exit MRI is within 2 months of the previous MRI scan, then an MRI does not need to be performed, except in the case that the previous MRI was performed prior to dosing and the early exit MRI will be the only MRI collected post IMP administration. The early exit MRI will be conducted in this instance.

6. RANDOMIZATION, BLINDING AND UNBLINDING

6.1 Randomization

At Screening Visit 1a subjects will be assigned a unique subject identification (ID) number that will be used throughout the study. The Investigator will maintain a list of subject ID numbers and names to enable records to be found at a later date.

Randomization will take place at Visit 2, before IMP administration. Randomization will be performed centrally, based on a pre-defined computer-generated randomization list accessed via an interactive response technology (IRT) system. The IRT system will ensure random allocation of eligible subjects in a 1:1 ratio to EP-104IAR 25 mg or vehicle treatment groups.

A statistician otherwise not involved in the trial will generate the randomization scheme. The randomization list will not be available to any person involved in the conduct and evaluation of the trial until the trial database is declared clean and locked.

6.2 Blinding

This is a double-blind study where subjects and assessors will be blinded to treatment allocation. Due to the impossibility of obtaining identical presentations of EP-104IAR and vehicle control, blinding at each site will be achieved by appointing 1 unblinded individual responsible for administering treatments and 1 blinded assessor who will perform all follow-up assessments. The blinded assessor should not be present at the time of injection.

Subjects will be blinded to treatment by shielding the subject's view of the IMP and the injection field.

The following laboratory test results could potentially enable blinded site staff to ascertain treatment allocation: morning serum cortisol and serum cortisol values following the ACTH stimulation test. Following randomization, these test results will not be included in the laboratory safety reports provided to the site, but instead will be sent separately to the Medical Monitor for review. The Medical Monitor will contact the Investigator to discuss appropriate steps for confirmatory testing and/or appropriate medical management of the subject if required. As the cortisol values selected to trigger ACTH stimulation testing in this study are deliberately conservative, a large proportion of both EP-104IAR and vehicle subjects will require this test simply due to their natural fluctuations in serum cortisol levels. Therefore, the requirement to perform an ACTH stimulation test does not indicate that a subject received EP-104IAR and vice versa.

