11 A serum pregnancy test will be performed on all women of childbearing potential at Screening. The sample collected for clinical chemistry analysis may be used for this purpose. A urine pregnancy test will be performed on all women of childbearing potential at Visit 2 and the End-of-Study (or Early Exit) visit. If the subject is participating in the optional imaging sub-study, the Visit 2 urine pregnancy test will be performed prior to performing the MRI. It does not need to be repeated prior to dosing.

12 HbA1c will be measured at Screening and End-of-Study (or Early Exit) visits.

13 To be collected at approximately the same time each visit, between 7-11 a.m. The clinical chemistry sample can be used for cortisol analysis, if being collected at the same visit.

14 Prior to and 2 hours after dosing. (For the 2 hour post-dose assessment a -15/+15-minute window is permitted.)

15 The ACTH stimulation test may be performed at any time of day and on any day during Screening, including at Visit 1b.

16 If the morning serum cortisol test result at Visit 6 (Week 8) is <350 nmol/L (<12.7 µg/dL) an ACTH stimulation test is to be performed at Visit 7 (Week 12). The site will be notified of this requirement in advance of the subject attending this visit.

17 For subjects whose ACTH stimulation test was abnormal at Visit 7, the test will be repeated at the End-of-Study (or Early Exit) Visit (the site will be notified of this requirement in advance of the subject attending this visit).

18 For those subjects not undergoing the ACTH stimulation test at Visit 9 (Week 24/Early Exit) if the result of the morning serum cortisol test at this visit is <350 nmol/L (<12.7 µg/dL), the site will be informed that an unscheduled visit is required to perform an ACTH stimulation test.

Notes:
ACTH=Adrenocorticotrophic hormone; AEs=Adverse events; Chem=Blood chemistry panel; Commed=Concomitant medication; ePRO=Electronic patient-reported outcome; Hem=Blood hematology panel; MDGA=Physician's Global Assessment of Arthritis; MRI=Magnetic resonance imaging; NPRS=Numerical pain rating scale; OA=Osteoarthritis; PK=Pharmacokinetic; PIgA=Patient's Global Assessment of Arthritis; SF-36=Short Form 36 questionnaire; WOMAC=Western Ontario and McMaster Universities Osteoarthritis Index.

IMAGING SUB-STUDY ADDITIONAL SCHEDULE OF EVENTS

Visit	1a Screening (Multiple days)	2 Baseline & Dosing	7	9 End-of-Study (or Early Exit Visit)	10 Imaging Follow-up
Study Week	-8 to -3	1	12	24	52

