- If the subject's serum cortisol is ≤ 138 nmol/L (≤ 5 μ g/dL) at **any visit** after dose administration **AND** they experience signs and symptoms of AI (see Section 10.2.5), perform the ACTH stimulation test at the **next scheduled visit**.

See [Figure 2](#) below.

During Screening, sites will receive serum cortisol results from the ACTH stimulation test directly from the central safety laboratory to determine subject eligibility. At all later timepoints serum cortisol results will be received by the unblinded Medical Monitor, who will inform the site which subjects should undergo the ACTH stimulation test. ACTH stimulation test results will be reported to the unblinded Medical Monitor for review.

[figure not shown]
Criteria for evaluating if the ACTH stimulation test response is normal or abnormal are provided in the Laboratory Manual.

If the results of the ACTH stimulation test are considered to be abnormal and the subject also displays symptoms of adrenal suppression, they should be managed accordingly and may require glucocorticoid replacement therapy (e.g., with physiologic hydrocortisone). If appropriate, such subjects should be referred to an Endocrinologist (or other appropriate specialist) for further evaluation and treatment.

The ACTH stimulation test is extremely sensitive (95% sensitivity and 97% specificity); however, this translates to a false positive result in approximately 1 out of every 20 tests. The ACTH stimulation test will be repeated at the End-of-Study Visit in any subjects with an abnormal test result at Week 12.

Subjects who are diagnosed with AI following dose administration should be managed by their Endocrinologist (or other appropriate specialist) until resolution. If the subject's AI is ongoing at their final scheduled study visit, the Investigator should follow-up with the subject approximately 3 months later, with at least 1 additional contact during that 3-month period.

Figure 2 Triggers for ACTH Stimulation Testing

Note: ACTH=Adrenocorticotrophic hormone Wk=Week.

Protocol No. EP-104IAR-201 - Version 7.0
15 Aug 2022

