9.1.8 Exploratory Assessments

9.1.8.1 Question on Treatment Received

Following completion of all other safety, PK and efficacy assessments at Visit 9 (End of study/Early-Exit Visit) the subject and the blinded assessor will each be asked the following question:

“Do you think (you/the subject) received the test medication or the placebo?” (Test medication / Placebo)

Why do you think this (check all that apply)?

- Knee pain
- Knee function
- Knee stiffness
- Quality of life
- Adverse effects
- Other (specify) _____

The responses to this question may be useful when interpreting any unusual or unexpected physician or patient-reported outcome measures.

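### Section 6.2 treats any call for an ACTH test as uninformative about treatment; that fails for the planned Visit 9 repeat, whose advance notice tends to disclose a withheld normal/abnormal result before the Week 24 physician rating and treatment guess

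*Protocol*

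**What the plan says.** Protocol section 6.2 introduces post-randomisation morning cortisol and ACTH-stimulated cortisol with the words "The following laboratory test results could potentially enable blinded site staff to ascertain treatment allocation", and for that reason "these test results will not be included in the laboratory safety reports provided to the site"; they go to the Medical Monitor. It then gives a single argument for why being called for a test carries no information. The argument opens "As the cortisol values selected to trigger ACTH stimulation testing in this study are deliberately conservative", adds that many subjects in both arms will meet the trigger through natural fluctuation, and ends with the conclusion that "the requirement to perform an ACTH stimulation test does not indicate that a subject received EP-104IAR and vice versa".

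The triggers are in the Schedule of Events footnotes and section 9.1.5.1.2:

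- **Visit 7 test** (footnote 16): "If the morning serum cortisol test result at Visit 6 (Week 8) is <350 nmol/L", a test is done at Visit 7.
- **Visit 9 repeat** (footnote 17, which also covers early exits): "For subjects whose ACTH stimulation test was abnormal at Visit 7, the test will be repeated at the End-of-Study". Staff are told before the subject attends.
- **Visit 9 cortisol below 350 nmol/L** (footnote 18): leads to a later unscheduled visit, not to a test at Visit 9.
- **Other routes**: cortisol of 138 nmol/L or lower with signs and symptoms of adrenal insufficiency, tested at the next scheduled visit (9.1.5.1.2); or clinically suspected adrenal insufficiency (10.2.5).

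The treatment-guess question is put to the subject and the blinded assessor "Following completion of all other safety, PK and efficacy assessments at Visit 9" (9.1.8.1).

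**The concern.** The argument in 6.2 is about a cortisol threshold that many subjects in both arms will cross. The Visit 9 repeat is not triggered by that threshold but by the result that 6.2 sets out to withhold. A site that holds the protocol and knows who was tested at Visit 7 can usually read a call for a repeat as an abnormal result, and no call as a normal one.

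The person who learns this may be the rater. Section 6.2 has the Medical Monitor contact the Investigator, section 9.1.5.1.2 has the Medical Monitor tell the site whom to test, and section 9 describes the blinded assessor as the Investigator or sub-Investigator. The MDGA is meant to draw on all the information to hand at the visit (9.1.7.7). The SAP compares MDGA between arms at Week 24 (3.8.2) and summarises the treatment guesses (3.8.3). Neither document describes a safeguard, such as restricted routing of the notice or a rater kept unaware of it.

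**Working it through.** **Trigger logic.** For a test done at Visit 9, the below-350 rule cannot supply masking cases, because it sends subjects to a later unscheduled visit. What remains is the repeat after an abnormal Visit 7 test and the two adrenal-insufficiency routes. None of these is the conservative trigger on which 6.2 relies.

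**Inputs from the documents.** Allocation is 1:1 (6.1). An abnormal screening ACTH test is exclusionary (5.3, criterion 26), so abnormal Week 12 tests on vehicle should be mostly false positives. On accuracy, section 9.1.5.1.2 states: "The ACTH stimulation test is extremely sensitive (95% sensitivity and 97% specificity", and then equates this with a false positive in about one test in 20. The two do not match: 1 - 0.97 = 0.03, about 1 in 33, whereas 1 in 20 is 1 - 0.95, one minus the sensitivity. Both 3% and 5% are carried below.

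**Assumptions.** The documents give no rate of testing at Visit 7 and no rate of abnormal tests on EP-104IAR. Assume 50% of vehicle subjects are tested (tV), 50-60% of EP-104IAR subjects (tE), and 5%, 10% or 20% of EP-104IAR tests are abnormal (pE). There is no plan figure to reproduce.

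**Formula.** P(EP-104IAR | repeat) = tE·pE / (tE·pE + tV·fp), where fp is the false-positive rate.

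| pE | fp = 3% | fp = 5% |
|---|---|---|
| 5% | 0.625-0.667 | 0.500-0.545 |
| 10% | 0.769-0.800 | 0.667-0.706 |
| 20% | 0.870-0.889 | 0.800-0.828 |

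Lowest cell: 0.5×0.05 / (0.5×0.05 + 0.5×0.05) = 0.500. Highest: 0.6×0.20 / (0.6×0.20 + 0.5×0.03) = 0.12/0.135 = 0.889.

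**Numbers affected**, at 150 per arm:

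- Vehicle: 150×0.5×0.03 = 2.25 to 150×0.5×0.05 = 3.75.
- EP-104IAR: 150×0.5×0.05 = 3.75 to 150×0.6×0.20 = 18.
- Share of 300: (2.25 + 3.75)/300 = 2.0% to (3.75 + 18)/300 = 7.25%.

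At 120 completers per arm the counts fall to 1.8-3.0 and 3.0-14.4; the share is unchanged.

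**Second parameterisation.** Let q be the true rate of adrenal insufficiency among tested EP-104IAR subjects, with equal testing in both arms, so pE = 0.95q + (1 - q)·fp. For q = 2%, 5%, 10% and 20%, P(EP-104IAR | abnormal) is 62%, 72%, 80% and 88% at fp = 3%, and 58%, 66%, 74% and 82% at fp = 5%. It is 50% only when q = 0. Among subjects tested at Visit 7, a normal result moves the probability only to 45-49.5%.

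**The case against.** Much of the case on the other side stands.

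- **What is disclosed.** The notice gives normal/abnormal status, not cortisol values, and a Visit 9 test can also arise from the two adrenal-insufficiency routes. A reader might infer that the call reveals allocation. It does not: false positives occur on vehicle, and at the protocol's 1-in-20 rate with 5% abnormal on EP-104IAR there is little or no leak. Section 2.2 anticipates no adverse effect on adrenal function, although section 2.1.2 expects that some cortisol perturbation may occur.
- **Which endpoints.** A reader might infer that the key secondary WOMAC Pain at Week 24 is compromised. The documents do not say that subjects are told the Visit 7 result or what a repeat means. WOMAC is completed before other site assessments, and so are SF-36 and the patient's global assessment (footnotes 8 and 9). That ordering separates the scores from the procedure but not from an earlier notice, so exposure is conditional on the subject learning of it.
- **Effect on results.** No bias is shown. If every affected MDGA rating moved by a full point in the same direction, the arm difference would shift by between (3.75 - 3.75)/150 = 0 and (18 - 2.25)/150 = 0.105 on a 0-10 scale.
- **The guess question.** It exists to detect loss of blinding, so a guess prompted by the notice does not make the question invalid. But a guess taken after the repeat describes blinding later than the moment of rating.
- **Safety contact.** Section 6.2 accepts that the Medical Monitor will speak to the Investigator about confirmatory testing and management. Any change must leave that intact.

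It can also be said that the 6.2 sentence, read in context, concerns only cortisol-triggered tests. It is worded for any ACTH test, however, and footnote 17 is not carved out. The trigger figure (Figure 2) is not reproduced in the text available, and the text does not name who at the site receives the notice.

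**Conclusion.** The 6.2 statement is sound for tests triggered by cortisol below 350 nmol/L and unsupported for the planned Visit 9 repeat. Advance notice of that repeat tends to disclose the status of a withheld result before the Week 24 MDGA (an additional secondary endpoint) and the treatment guess (exploratory).

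The size is small: about 2-7% of subjects, with P(EP-104IAR | repeat) from about 50% (5% abnormal, 1-in-20 false positives) to about 89% (20% abnormal, 3% false positives). These figures depend on assumed testing and abnormality rates. If EP-104IAR produces no excess of abnormal tests, the signal disappears.

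The Week 12 primary endpoint is not affected by this route: the Visit 7 test uses the conservative trigger, and the notice of a repeat comes only after that test has been read. This is an avoidable route to partial unblinding that should be closed because closing it is cheap; it is not a threat to the main result.

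**What to change.** 1. In section 6.2, limit the statement to tests triggered by the 350 nmol/L cortisol threshold, and reconcile it with footnote 17 and section 9.1.5.1.2.
2. In footnote 17 and section 9.1.5.1.2, send the routine scheduling notice for the Visit 9 repeat to the unblinded individual already appointed at each site, not to the blinded assessor.
3. Record the Visit 9 MDGA, the patient-reported scores and the treatment-guess question before the repeat is disclosed or done. Section 9.1.8.1 must be amended to match, because it now places the question after all other safety assessments.
4. Leave the test criteria and the Medical Monitor's contact with the Investigator for medical management unchanged. Where that contact has occurred before the Week 24 ratings, record it, and have the SAP examine MDGA and the guess data with and without those subjects.

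The cost is wording, notice routing and one recorded item. The unblinded individual must be available at Visit 9 for a few subjects. Section 9.1.5.1.2 requires no fasting and allows the test at any time of day, so it can follow the ratings.

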6.3 Unblinding

Users assigned unblinded roles within the IRT system will have access to randomization details for all randomized subjects at their site. In the event of an emergency (e.g., an SAE that requires knowledge of treatment, or a pregnancy), the PI may access the IRT system to unblind a single subject. The PI should make every effort to contact the Sponsor or the Medical Monitor before the blind is broken; otherwise, the Medical Monitor will be notified

as soon as possible. In addition, the Institutional Review Board (IRB)/Independent Ethics Committee (IEC) will also be notified of any emergency unblinding during the study. Emergency unblinding will be documented in the IRT system. The date and reason that the blind was broken must be recorded in the source documentation and case report form, as applicable.

If breaking the blind is considered necessary for other safety reasons, for example due to signals of alerting adverse drug reactions (ADRs) and regulatory reporting of SUSARs, unblinding can be performed by the Sponsor without compromising blinded members of the trial team, and the reason for unblinding should be documented.

Imaging Sub-Study

Details concerning data management in the imaging sub-study will be described in the Data Management Plan and other appropriate study specific documents. The planned unblinding and analysis of the main study will not be impacted by the ongoing imaging sub-study. All MRI central readers will be blinded to treatment allocation and study visit for the entirety of the imaging sub-study.

7. STUDY TREATMENTS

Detailed instructions on the storage, preparation, administration and accountability requirements for the IMP and non-investigational medicinal products (NIMPs) will be provided in the IMP Handling Manual.

7.1 IMP Dosage Forms/Formulation

All IMP used in this study have been manufactured in accordance with current Good Manufacturing Practice.

7.1.1 EP-104IAR

The EP-104IAR investigational medicinal product is a two-vial system (see Parts A and B in Table 1):

- **Part A:** (EP-104IAR Powder) a sterile powder containing cured PVA-coated FP crystals.
 - FP crystals are coated with biocompatible polymer, PVA, and then heat-treated to crosslink the polymer and form long-acting particles designed to release FP over several months. The PVA membrane represents less than 10% of the drug product composition.
 - Each single use vial of EP-104IAR Powder contains a sufficient quantity of powder to deliver a dose of 25 mg of FP. A small overage is included in each vial to account for losses to the vial and syringe during constitution prior to injection.
- **Part B:** (vehicle) a sterile liquid containing sterile water and excipients necessary to prepare a uniform suspension of the powder.
 - Each single use vehicle vial includes a 1 mL overage to account for losses during the vehicle transfer and powder suspension constitution process.

The EP-104IAR Powder is suspended in the sterile vehicle immediately prior to IA injection. Instructions for the constitution procedure are provided in the IMP Handling Manual.

7.1.2 Vehicle Control

The placebo control used in this study is 5 mL of vehicle (Part B in [Table 1](#)). Vehicle is provided as bulk supplies of single use bottles, containing 6 mL of vehicle and labeled for use in this study.

Table 1 Composition of EP-104IAR

PART A. EP-104IAR Powder		
Component	Function	mg Label Claim (mg Including Overage)¹
Fluticasone Propionate, USP	API	25.0 (30.0)
Polyvinyl Alcohol, USP	Release modifier	1.6 (1.9)
PART B. Vehicle		
Component	Function	mg
Carboxymethyl Cellulose, USP	Viscosity builder	37.5
Polysorbate 80, NF	Suspending agent	0.75
Sodium Chloride, USP	Isotonicity	41.0
Sodium Phosphate Dibasic Heptahydrate, USP	Buffer	10.90
Sodium Phosphate Monobasic, USP	Buffer	1.30
Water for Irrigation, USP	Solvent	QS to 5.00 mL
Total Volume		5 mL²

1 A small overage is included in each vial to account for losses during constitution prior to injection.

2 Vials are filled with 6 mL to ensure 5 mL can be withdrawn and used to constitute the powder prior to injection.

Notes: API=Active pharmaceutical ingredient; NF=National Formulary; QS=Quantum Sufficit (a sufficient quantity); USP=United States Pharmacopeia.

